Our specific aims are:

1. To examine the rate of respiratory failure requiring reintubation and invasive mechanical ventilation (IMV) within 72 hours of initiating study intervention.
2. To examine the rate of respiratory failure requiring reintubation and IMV within 7 days of transitioning off of non-invasive study intervention
3. To compare the total number of days requiring intubation with mechanical ventilation
4. To compare the rates of moderate to severe BPD with and without altitude correction at 36 weeks CGA per criteria defined by 2001 NICHD Consensus Conference

E. Methods

1. **Trial design:** This is a prospective, randomized trial.
2. **Study site:** The study site will be the University of Utah Medical Center, a Level III neonatal intensive care unit with 52 beds.
3. **Population:** Infants born $24^{0/7}$ to $28^{6/7}$ weeks gestational age (GA) requiring invasive mechanical ventilation (IMV) and meet extubation criteria within the first 7 days of life
 - a. **Inclusion criteria:**

- i. $24^{0/7}$ to $28^{6/7}$ weeks GA
- ii. Intubated within 24 hours of life to synchronized intermittent mandatory ventilation (SIMV) or high frequency ventilation (HFV, includes HFOV or HFJV)
- iii. Meets unit guidelines for extubation within 7 days of life
 - 1. See Table 1 for outline of criteria
- iv. Infants intubated for surfactant replacement therapy via INSURE method (Intubation-Surfactant-Extubation) are eligible
- v. Initiation of treatment arm must occur within 6 hours of extubation
 - 1. If randomization occurs after the time of extubation, infants are eligible if FiO_2 requirements are $>30\%$
- vi. Consent obtained from parent/legal guardian

b. **Exclusion criteria:**

- i. Major congenital and/or chromosomal anomalies
- ii. Upper oropharyngeal anomalies

4. Randomization:

- a. Infants stratified by GA ($24^{0/7}$ – $25^{6/7}$ weeks, $26^{0/7}$ – $28^{6/7}$ weeks) and randomized in blocks of 4 to nHFJV or NIPPV group
- b. Randomization and initiation of treatment arm must occur within 6 hours of extubation
- c. Randomization will occur via sealed opaque envelopes

5. Intervention: Subjects will be randomized to be extubated to nasal HFJV (nHFJV) via the Bunnell Life Pulse high-frequency JET ventilator through a latex free PVC nasopharyngeal airway.

- a. Initial settings for nHFJV:
 - i. PEEP = 8
 - ii. HFJV PIP = 25
 - iii. On-time = 0.034 second
 - iv. Rate = 360 breaths per minute
 - v. Conventional rate = 10 breaths per minute

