 - i. Blood gases ordered per clinical practice
- c. Randomized infants extubated to nHFJV or NIPPV
 - i. Nasopharyngeal airway to be replaced in alternating nares every 48 hours to decrease risk of skin breakdown
- d. Respiratory settings adjusted to maintain target blood gas and/or TCM values
 - i. Goal: pH >7.2, PaCO₂ 45-60 mmHg, PaO₂ 60-80 mmHg
 - ii. Adjustment of nHFJV support as indicated in Table 2
 - iii. Adjustment of NIPPV support as indicated in Table 3
- e. Record vital signs (heart rate, respiratory rate, blood pressure) and ventilator support, including FiO₂, TCM/PaCO₂ and Silverman score for the first 24 hours of study support as follows: every 1 hour for three recordings then every 3 hours for three recordings and then every 6 hours for two recordings. Subsequently we will record this data every 12 hours until 48 hours and then every 24 hours for the remaining 7 days of the study period.
- f. Infant can be transitioned to CPAP via binasal prongs and/or mask when on minimal settings of the respiratory intervention for \geq 24 hours with acceptable oxygen saturations and TCM
 - i. Minimal nHFJV settings
 1. PEEP of 6, IMV rate of 0, HFJV PIP of 15, HFJV rate of 360 breaths per min, FiO₂ \leq 0.3

2. Transition to CPAP of 6 cm H₂O
 - ii. Minimal NIPPV settings
 1. PEEP of 5, PIP of 15, rate of 5 breaths per minute
 2. Transition to CPAP of 6 cm H₂O
 - iii. At the discretion of the attending physician, infant can be placed on bubble CPAP (bCPAP) or ventilator-interface CPAP.
- g. Criteria for termination of non-invasive study mode:
 - i. Respiratory failure meeting reintubation criteria as noted above
 - ii. At the request of the attending physician and/or parent/legal guardian
 - iii. Upon transfer of infant to Primary Children's Hospital for non-respiratory medical/surgical care
- h. Continue study respiratory intervention for 7 days, after which the respiratory support will be transitioned from nHFJV to another respiratory support modality of the attending physicians choosing.

9. Statistical Analysis: Data will be de-identified and analyzed on an intent to treat basis.

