

Table 1. Unit guidelines for extubation criteria

WEIGHT (grams)								
	< 1000	1000-2000	2000-3000	> 3000				
MAP	8	9-10	10-12	12				
Amp	16	18	20	22				
FiO ₂	< 0.4							
HFOV								
WEIGHT (grams)								
	< 1000	1000-2000	2000-3000	> 3000				
PIP	< 16	16-20	20					
PEEP	< 6	< 7	< 8					
PS	< 6 – 8							
FiO ₂	< 0.4							
Rate	16 – 20							
PC-SIMV and PC-PSV								
WEIGHT (grams)								
	< 1000	1000-2000	2000-3000	> 3000				
PIP	< 16	16-20	20					
PEEP	< 6	< 7	< 8					
VT	4 – 5 ml/kg							
PS	< 6 – 8							
FiO ₂	< 0.4							
Rate	16 – 20							
SIMV + VG and PSV + VG								

Table 2a. Adjustment of nHFJV support

In order of preference:	
Improving PaO ₂	
 1. Wean FiO₂ until ≤ 0.3 2. Wean PEEP by 1 cm H₂O to a minimum of 6
Improving PaCO ₂	
 1. Wean IMV PIP by 1-2 every 3-4 hours to a minimum of 15 cm H₂O 2. Wean IMV rate by 2 every 3-4 hours to off 3. Wean HFJV PIP by 1-2 every 3-4 hours to minimum of 15 cm H₂O
Worsening PaO ₂ and FiO ₂ > 0.4	
 1. Increase PEEP by 1-2 cm H₂O every 15 minutes to maximum of 12 cm H₂O 2. If no chest rise with IMV breaths, increase IMV PIP by 1-2 cm H₂O to a maximum of 30 cm H₂O
Worsening PaCO ₂	
 1. Increase HFJV PIP by 2-3 cm H₂O until visible chest wiggle to maximum of 30 cm H₂O 2. If no effect, increase HFJV rate by 60 bpm to maximum of 480 bpm 3. If no effect, increase IMV PIP by 1-2 cm H₂O every 30-60 minutes to maximum of 30 cm H₂O 4. If no effect, increase IMV rate by 1-2 bpm to maximum of 20 bpm

Table 2b. Caveats of care with nHFJV support

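### Step-down to CPAP requires FiO₂ ≤0.3 for nHFJV but sets no FiO₂ limit for NIPPV, so the start of the Aim 2 window can depend on arm

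*Combined protocol and SAP*

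**What the plan says.** The stem of E.8.f applies to both arms: "Infant can be transitioned to CPAP via binasal prongs and/or mask when on minimal settings of the respiratory intervention for" at least 24 hours, provided saturations and transcutaneous readings are acceptable. It puts no number on acceptable.

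Minimal settings are then defined by arm:

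- nHFJV (E.8.f.i): "PEEP of 6, IMV rate of 0, HFJV PIP of 15, HFJV rate of 360 breaths per min, FiO₂ \leq 0.3"
- NIPPV (E.8.f.ii): "PEEP of 5, PIP of 15, rate of 5 breaths per minute"

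Both arms go to CPAP of 6 cm H₂O.

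Aim 2 (Section D, repeated in E.7.b) is "To examine the rate of respiratory failure requiring reintubation and IMV within 7 days of transitioning off of non-invasive study intervention". The other ways off the study mode that matter here are a request under E.8.g.ii ("At the request of the attending physician and/or parent/legal guardian") and the end of the study period under E.8.h ("Continue study respiratory intervention for 7 days, after which the respiratory support will be transitioned from nHFJV").

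Tables 2a and 3 each list, as an order of preference when oxygenation improves, FiO₂ down to 0.3 or less and then PEEP. For nHFJV the second step is "Wean PEEP by 1 cm H₂O to a minimum of 6"; for NIPPV the PEEP floor is 5. Both tables call for more oxygenation support only when FiO₂ is above 0.4.

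**The concern.** Aim 2 is counted from the moment an infant leaves the study mode, and E.8.f is the planned way to leave before day 7. A condition that is written for one arm only can make entry to that seven-day window depend on allocation. An infant on otherwise minimal settings at FiO₂ 0.31–0.40 may start the clock if allocated to NIPPV, but not under E.8.f if allocated to nHFJV. The infants observed after early step-down could then differ between arms in oxygen need, and in how long they had been on study support. The protocol gives no reason for the difference and describes no masking, so bedside staff apply the rule knowing the allocation.

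**Working it through.** **Step 1. Does anything else supply the missing limit?**

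| Provision | nHFJV | NIPPV |
|---|---|---|
| FiO₂ term in minimal settings (E.8.f.i, E.8.f.ii) | ≤0.3 | none |
| Acceptable saturations and transcutaneous readings (E.8.f stem) | yes | yes |
| Preferred weaning order (Tables 2a, 3) | FiO₂ to ≤0.3, then PEEP | FiO₂ to ≤0.3, then PEEP |
| Oxygenation escalation (Tables 2a, 3) | FiO₂ >0.4 | FiO₂ >0.4 |

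The stem does not supply it. E.5 and E.6 have FiO₂ adjusted to reach target saturations, so saturations can be acceptable at any FiO₂ that achieves them.

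Table 3 supplies it in part. Controls start at PEEP 6 and need PEEP 5, so a control weaned in the preferred order reaches FiO₂ ≤0.3 first. Nothing requires FiO₂ to stay there for the 24 hours or at the transition, and 0.31–0.40 triggers no escalation. That leaves mainly the controls who drift back into this range.

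**Step 2. Time to step-down from the written settings.** Inputs are the initial settings in E.5 and E.6, the minimal settings in E.8.f, and the weaning steps in Tables 2a and 3. Assumptions: first step one interval after the start, no setbacks, and PEEP weaned alongside because no interval is given for it.

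Step-down time = (number of steps × interval) + 24 h. Fastest is 2 cm H₂O every 3 h; slowest is 1 cm H₂O every 4 h.

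- NIPPV: PIP 25 to 15 and rate 20 to 5 in fives. Fastest (5 + 3) × 3 + 24 = 48 h. Slowest (10 + 3) × 4 + 24 = 76 h.
- nHFJV, ladder A, full listed order. Table 2a's first step is "Wean IMV PIP by 1-2 every 3-4 hours to a minimum of 15 cm H₂O", so IMV PIP goes 24 to 15, then IMV rate 10 to 0 in twos, then HFJV PIP 25 to 15. Fastest (5 + 5 + 5) × 3 + 24 = 69 h. Slowest (9 + 5 + 10) × 4 + 24 = 120 h.
- nHFJV, ladder B, without the IMV PIP step, which E.8.f.i does not require. Fastest (5 + 5) × 3 + 24 = 54 h. Slowest (5 + 10) × 4 + 24 = 84 h.

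**Step 3. What the FiO₂ rule adds.** Take an nHFJV infant at FiO₂ 0.31–0.40 from the time the other settings become minimal until day 7 (168 h), with no earlier termination under E.8.g.

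- Ladder A: 168 − 120 = 48 h to 168 − 69 = 99 h.
- Ladder B: 168 − 84 = 84 h to 168 − 54 = 114 h.

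A matching control may leave at 48–76 h if the 72-hour Hudson prong rule in E.6.g governs only the interface for NIPPV, or at 72–76 h if it also bars earlier CPAP.

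**Step 4. What the rule does not explain.** For infants at FiO₂ ≤0.3 throughout, the rule changes nothing. A gap from the weaning ladders remains: 69 − 48 = 21 h to 120 − 76 = 44 h with ladder A, or 54 − 48 = 6 h to 84 − 76 = 8 h with ladder B.

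**Step 5. Set mean pressure at step-down** (square wave, leak ignored, inspiratory time 0.6 s and on-time 0.034 s unchanged).

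- NIPPV: 5 × 0.6 = 3 s per minute at PIP, so (3 × 15 + 57 × 5)/60 = 5.5 cm H₂O.
- nHFJV: 360 × 0.034/60 = 0.204, so 0.204 × 15 + 0.796 × 6 = 7.8 cm H₂O.

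Moving to CPAP 6 therefore lowers set mean pressure for nHFJV and raises it slightly for NIPPV.

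**The case against.** The strongest reply is that the difference may be sensible. By step 5, an nHFJV infant loses set mean pressure on moving to CPAP and a control does not. The nHFJV infant also changes from a nasopharyngeal airway to prongs or mask, while controls start on prongs. An oxygen guard is more natural where support falls. Minimal settings already differ by arm, and the trial compares two support strategies, each with its own weaning rules. On the same figures, the fix would hold some controls at a set mean pressure of 5.5 rather than CPAP 6. Table 3 brings most controls to FiO₂ ≤0.3 anyway, and E.8.f permits step-down without requiring it.

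Much of this stands. It keeps the point small and rules out any claim of harm. It does not close the gap, because the protocol states no such rationale and the start of the Aim 2 window still depends on arm. Nor can Table 3's order simply stand in for a limit: Table 2a has the same order, yet E.8.f.i also states the limit. That could be mere redundancy, so it is supporting evidence only.

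A reader might infer three stronger things that the documents do not support:

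- That controls step down with no oxygen condition at all. The stem's saturation condition applies to them; what is missing is an FiO₂ limit.
- That the rule biases the reintubation comparison in a known direction. Nothing gives the FiO₂ distribution at step-down or the effect of stepping down at 0.31–0.40.
- That Aim 1 is undermined. Its 72 hours run from the start of the intervention, so its time origin does not depend on this rule. Control CPAP inside that window at this FiO₂ is possible only if E.6.g is an interface rule.

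**Conclusion.** The asymmetry is in the current text and no other provision removes it. It affects only infants who leave, or would otherwise leave, by E.8.f, and mainly those who drift back to FiO₂ 0.31–0.40. For them, the start of the Aim 2 window depends on arm. The number of such infants is not given, and the effect on reintubation may be zero. The waits of 48–99 h and 84–114 h are illustrations for one constructed course; they rest on the assumed ladder and on FiO₂ staying in that range until day 7. This is a minor, cheap improvement that rests on consistency and not on demonstrated bias.

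**What to change.** Add FiO₂ ≤0.3 to the minimal NIPPV settings in E.8.f.ii.1, or move the limit from E.8.f.i to the stem of E.8.f so that it applies to both arms. The threshold is the sponsor's own: it is Table 3's weaning target, and E.3.a.v uses 30% without regard to arm for infants randomized after extubation. If the difference is deliberate, one sentence giving the reason would make that clear, although the window would still start under different rules.

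The cost is one phrase by amendment. FiO₂ is already recorded under E.8.e, though only every 24 hours after 48 hours, so the 24-hour hold is judged at the bedside, as it already must be for nHFJV. The downside is that a few controls stay longer on minimal NIPPV. The change does not remove the timing difference that comes from the weaning ladders.

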Statistical analysis will be performed using SPSS (version 25, IBM, Armonk, NY). The primary outcome and other categorical measures will be analyzed by Chi-square or Fisher's Exact test. Student's *t* test will be used for analysis of normally distributed continuous data and Mann-Whitney *U* test will be applied for ordinal data or continuous data that is not normally distributed. Two-sided P values of less than 0.05 will be considered to indicate statistical significance, and no adjustments will be made for multiple comparisons

10. Population and Recruitment Time:

- a. Approximately 60 infants born 24 0/7 to 28 6/7 weeks GA are born at the UUMC NICU each year
 - i. Estimated sample size is 40 infants (n=20 per group) This is a pilot study designed to test feasibility and safety of the nHFJV. However, the sample size proposed may allow identification of possible significant benefits. Based on historical failure rates in this patient population, including a recent study from Zhu et al, the estimated failure approaches 50% with the current standard. If we were able to show a reduction in that failure rate by 50% (from 50% to 25%, as shown in the Zhu, et al study) we would approach a P value of 0.05 by Chi-squared analysis.
 - 1. Zhu X-W, et al. Pediatric Pulmonology, 2017; 52(8)
- b. Expected time to complete study from initiation through closeout is approximately 2 years.

F. Risks and Benefits

NIPPV is a routine and well known mode of respiratory support with a few known risks, including air leaks, gaseous distension/discomfort and skin breakdown at the site of the prongs/mask. Effort is made to decrease the gaseous distension by allowing the enteric tube placed for enteral feeds to vent periodically throughout the day. We do not anticipate higher risk in the patients randomized to the nHFJV group. The nasopharyngeal airway will be replaced in alternating nares in the nHFJV group every 48 hours to decrease the risk of skin breakdown.

Potential benefits to study participants assigned to the nHFJV group may include decreased risk of reintubation and decreased days requiring mechanical ventilation. This improvement may translate to decreased severity of BPD at 36 weeks CGA. Benefits to society include increased

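### Randomisation is stratified by two gestational-age bands, but section E.9 tests the primary outcome with a pooled test: valid, but possibly inefficient if gestational age is strongly prognostic

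*Combined protocol and SAP*

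**What the plan says.** Section E.4.a (Randomization): "Infants stratified by GA", in two bands split at 26 weeks, and "randomized in blocks of 4 to nHFJV or NIPPV group".

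Section E.9 (Statistical Analysis): "Data will be de-identified and analyzed on an intent to treat basis". For binary outcomes, "The primary outcome and other categorical measures will be analyzed by Chi-square or Fisher's Exact test". Continuous outcomes get a two-sample *t* test, and the Mann-Whitney "test will be applied for ordinal data or continuous data that is not normally distributed". Significance is judged two-sided at 0.05. No stratified test, GA covariate or adjusted model appears anywhere in the protocol, and nothing says that pooling over the bands is deliberate.

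Section E.10.a gives the size and target: "Estimated sample size is 40 infants (n=20 per group"), with failure falling from 50% to 25%, where "we would approach a P value of 0.05 by Chi-squared analysis". On recruitment it says "Approximately 60 infants born 24 0/7 to 28 6/7 weeks GA are born at the UUMC NICU each year", with no split by GA band.

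E.9 does not say which aim is primary. Aim 1 (reintubation within 72 hours) is the likely reading, because it comes first and the reintubation criteria are listed only under it.

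**The concern.** GA band is the only stratification factor. That choice makes most sense if GA is expected to predict reintubation. Stratified blocks then balance the arms on GA, so the treatment difference varies less from trial to trial than a pooled test assumes. The pooled test's variance is too large, its real type I error falls below 5%, and it cannot turn the balance into power. A test that conditions on the bands can.

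The stake is modest but not empty. The plan applies a formal significance rule to 40 infants and hopes that a benefit might show, with power of about 37% at its own target. At that level a few points matter, and so does leaving the test open between two that differ by more than 10 points.

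**Working it through.** **1. The plan's own figure.** With 10/20 vs 5/20 failures, chi-square = 40 × (10×15 − 5×10)² / (20×20×15×25) = 2.667, two-sided P = 0.102. Only the one-sided value (0.051) is near 0.05, and the plan is two-sided. That is a separate matter; what follows does not depend on it. Power at 50% vs 25% with 20 per arm is 37% by the normal approximation and 37.5% by exact enumeration of uncorrected chi-square.

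**2. Inputs.** From the protocol: two bands, 20 per arm, 50% vs 25%, two-sided 0.05. Assumed, because the protocol gives neither: 8 infants per arm in the younger band and 12 in the older, and a gap *g* in control risk between bands. Holding control failure at 50% overall, the younger band has 0.5 + 0.6*g* and the older 0.5 − 0.4*g*. Two effect shapes are used: each band's risk halved, or each reduced by 25 points. Both give 25% overall; at *g* = 50 points, 0.4×40% + 0.6×15% = 25% and 0.4×55% + 0.6×5% = 25%.

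**3. Why the pooled test becomes conservative.** In large samples its size is 2[1 − Φ(1.96/√r)], where r is the mean within-band variance divided by the total variance. At 80%/30%: r = (0.4×0.8×0.2 + 0.6×0.3×0.7)/(0.5×0.5) = 0.19/0.25 = 0.76, so the size is 2[1 − Φ(2.25)] = 2.5%.

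**4. Exact enumeration.** CMH = [Σ(aₖ − nₖmₖ/Nₖ)]² / Σ[n₁ₖn₀ₖmₖ(Nₖ − mₖ)/(Nₖ²(Nₖ − 1))], without continuity correction. Here aₖ is the failures in one arm of band k, nₖ (= n₁ₖ) that arm's size and n₀ₖ the other's, mₖ all failures and Nₖ all infants in the band. Results in %, 8+12 per arm:

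| Gap (points) | Control risks | Type I: chi-sq | Type I: CMH | Power, halved: chi-sq | CMH | Power, −25 points: chi-sq | CMH |
|---|---|---|---|---|---|---|---|
| 0 | 50/50 | 4.3 | 4.2 | 37.5 | 35.4 | 37.5 | 35.4 |
| 10 | 56/46 | 4.1 | 4.2 | 37.5 | 35.5 | 37.4 | 35.6 |
| 20 | 62/42 | 3.8 | 4.4 | 37.3 | 36.2 | 37.1 | 37.0 |
| 30 | 68/38 | 3.3 | 4.6 | 37.1 | 37.6 | 36.6 | 39.5 |
| 40 | 74/34 | 2.7 | 4.9 | 36.8 | 39.6 | 35.8 | 43.0 |
| 50 | 80/30 | 1.9 | 4.9 | 36.3 | 42.1 | 34.5 | 48.0 |

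Break-even is at about 20 points with the constant reduction. With halving it is about 27 (20 + 10 × 1.1/(1.1 + 0.5)).

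**5. Other splits and incomplete blocks.** With halving, CMH minus chi-square power at gaps of 20/30/40 points is −1.7/−0.6/+0.9 (4+16), −0.8/+0.6/+2.6 (6+14) and −0.3/+1.5/+3.9 (10+10). So a very uneven split moves break-even past 30. With blocks of 4, random band totals and 40% of infants assumed in the younger band, the difference at gaps of 0/20/30/50 is −1.7/−0.6/+1.0/+5.9, with break-even at about 24. CMH type I error stays at 4.3 to 4.9% there; the highest value at any fixed split is 5.1% (4+16, 50-point gap).

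**6. Which version of each test.** With continuity correction, CMH power (8+12, halved) is only 24.2% at gap 0 and 28.7% at gap 50, below pooled chi-square at every gap. Fisher's test at 50% vs 25% has 26.9% against 37.5% for uncorrected chi-square. Over the 441 possible pooled 20 vs 20 tables the two disagree in 28, and in none is Fisher's test alone significant.

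**The case against.** The strongest reply is that both tests are valid and that section E.10.a describes a pilot of feasibility and safety, for which a simple unadjusted comparison is defensible. The stratified test is also not uniformly better. At 8+12 with halving it loses 2.1, 2.0 and 1.1 points at gaps of 0, 10 and 20, and a gain above 3 points needs a gap over 40. All infants must meet the same extubation guideline, which may narrow the GA gap. The protocol cannot show which side of break-even applies. All of this stands, and it is why the point is an inexpensive improvement and not an error.

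Three stronger readings are tempting, and the documents do not support them.

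- *That ignoring the strata biases the comparison or inflates false positives.* The pooled size falls as GA becomes more prognostic. With no GA effect, exact chi-square size peaks at only about 5.3%. The open choice between chi-square and Fisher's test does not inflate error above that of uncorrected chi-square either (step 6).
- *That pooling throws away a lot of power.* With halving, pooled power moves only from 37.5% to 36.3% over the whole range. The difference at large gaps is almost all CMH gaining.
- *That every analysis in E.9 is shown to suffer.* For ventilator days and other continuous outcomes the protocol gives no inputs from which a loss could be sized.

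A practical objection also stands in part. The plan uses SPSS 25, and the protocol does not show that it returns the uncorrected CMH statistic. That must be confirmed before the wording is changed.

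**Conclusion.** The mismatch between E.4.a and E.9 is real. It is a conditional point of efficiency: CMH costs about 2 points of power if GA is not prognostic, breaks even at a control-risk gap of roughly 20 to 30 points for most splits tried, and at a 50-point gap gains about 6 points (risks halved) or about 13 (constant 25-point reduction). At 8+12 it holds type I error at 4.2 to 4.9%, while pooled chi-square drifts from 4.3% to 1.9%.

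The direction is secure. The sizes rest on assumed band sizes, band risks and effect shape, none of which the protocol gives. A reader might infer that stratifying would rescue the trial's power; at 40 infants it does not. The sponsor should make the change or state that pooling is deliberate, and in either case name one test.

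**What to change.** In E.9, replace the choice between chi-square and Fisher's test for the primary outcome with wording such as: *The primary outcome (reintubation within 72 hours, Aim 1) is tested with a single Cochran-Mantel-Haenszel test stratified by the two GA bands used at randomisation, without continuity correction. This test decides significance. A Mantel-Haenszel risk difference with 95% confidence interval is reported as descriptive.* The reference to Aim 1 applies if that is the sponsor's intent.

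Before adopting it, confirm that the software gives the uncorrected statistic. If only the corrected one is available, the change would do harm.

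If the sponsor prefers a pooled test, say so and name uncorrected chi-square in advance.

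Cost: analysis wording and a software check. The band is already known at randomisation, so no new data are needed. The downside is up to about 2 points of power if GA turns out to be weakly prognostic.

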Using a mechanical newborn lung model, nasal HFV has improved CO₂ removal when compared to conventional NIPPV (Mukerji et al, 2013; Mukerji et al, 2015). Animal studies in the lab of [name] have shown improved ventilation and oxygenation in the high frequency nasal ventilation group versus the mechanical ventilation group in a preterm lamb model leading towards better alveolar formation noted histologically (Reyburn et al, 2008; Null et al, 2014).

Few small clinical studies have looked at the use of nasal HFV however many were for short periods of time. Preterm infants on CPAP showed a significant decrease in pCO₂ after being switched to nHFV for a two hour period (Colaizy et al, 2008). In a pilot trial investigating the use of nasal HFV immediately after extubation in high-risk preterm infants, it was noted that pCO₂ levels significantly decrease, although returned to pre-extubation values after discontinuing nasal HFV (Czernik et al, 2012). In a recent randomized controlled trial, 81 infants were randomized to nasal HFV or nasal CPAP following surfactant administration (Zhu et al, 2017). Infants in the nasal HFV group had a significantly decreased need for invasive mechanical ventilation compared to the nasal CPAP group, however their cohort had a mean gestation age of ~32 weeks (Zhu et al, 2017). None of these clinical studies noted any negative impact from using nasal HFV.

C. Significance and Purpose

Very low birth weight infants are at increased risk of requiring prolonged duration of mechanical ventilation and multiple intubations, both of which are risk factors for ventilator-induced lung injury and BPD. Thus, it is important to investigate respiratory support methods that are able to effectively oxygenate and ventilate these high risk preterm infants while reducing their risk of lung injury. Nasal high-frequency ventilation is one potential intervention that may decrease the risk of respiratory failure in very low birth weight infants. Small studies have shown effective respiratory support over short time periods in infants, however these studies use nasal high-

frequency oscillatory ventilation. To our knowledge there are no published studies looking at the use of nasal high-frequency jet ventilation in this high risk population.

D. Hypothesis and Specific Aims

We hypothesize that extubation of very preterm infants to nHFJV will significantly decrease the rates of reintubation compared to those infants extubated to NIPPV.

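### The sample-size justification misstates its P value: 50% versus 25% failure with 20 infants per group gives two-sided P = 0.10 by chi-square (0.19 by Fisher), not a value near 0.05

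*Combined protocol and SAP*

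**What the plan says.** Section E.10 (item a.i) sets the size at 40 infants, 20 per group, and gives its status: "This is a pilot study designed to test feasibility and safety of the nHFJV". It then adds that "the sample size proposed may allow identification of possible significant benefits". The support for that addition is a control failure rate approaching 50%, a fall by half to 25% taken from a cited randomized trial, and the statement that with this result "we would approach a P value of 0.05 by Chi-squared analysis". No power is stated.

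Section E.9 gives the rules for the analysis. "The primary outcome and other categorical measures will be analyzed by Chi-square" or by Fisher's exact test, and "Two-sided P values of less than 0.05 will be considered to indicate statistical significance".

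E.10 introduces its rates with the words "Based on historical failure rates in this patient population, including a recent study". Section B describes that same study as a comparison of nasal high-frequency ventilation with nasal CPAP, and notes of the "nasal CPAP group, however their cohort had a mean gestation age of ~32 weeks".

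**The concern.** Everything needed to check the P value is printed in E.9 and E.10, and at 20 per group the two rates give whole counts, so rounding cannot explain a discrepancy. A reader of E.10 would conclude that the assumed benefit, if observed, puts the trial at the edge of significance. If the true P value is well above 0.05, the sentence gives too favourable a picture of what 40 infants can show.

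The stake is interpretation. Section D hypothesises a significant decrease in reintubation, and E.9 commits to a test at two-sided 0.05. A team or reader relying on E.10 could take a non-significant result as evidence against nHFJV, when that is the more likely outcome even if the assumed effect is real.

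A secondary point concerns the rates themselves. The trial cited for the 25%, and in part for the 50%, had a different comparator (CPAP, not NIPPV) and an older population (mean about 32 weeks, against 24 to 28 weeks here). E.10 does not repeat this, although section B does.

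**Working it through.** **Inputs.** 20 per group, control failure 50% and nHFJV failure 25% (E.10); chi-square or Fisher's exact test, two-sided, threshold 0.05 (E.9). The implied table is:

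| | Failure | No failure | Total |
|---|---|---|---|
| NIPPV | 10 | 10 | 20 |
| nHFJV | 5 | 15 | 20 |
| Total | 15 | 25 | 40 |

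**Step 1: the plan's own figure.** Expected counts per arm are 20 × 15/40 = 7.5 failures and 20 × 25/40 = 12.5 non-failures. Each cell differs from expectation by 2.5, so

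chi-square = 2 × (2.5² / 7.5) + 2 × (2.5² / 12.5) = 1.667 + 1.000 = 2.667 on 1 df.

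The two-sided P is 0.1025. The stated value is not reproduced.

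**Step 2: other versions of the test on the same table.**

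| Test | Two-sided P | One-sided P |
|---|---|---|
| Pearson chi-square, uncorrected | 0.102 | 0.051 |
| Likelihood-ratio chi-square | 0.100 | – |
| Unpooled z | 0.091 | – |
| Chi-square with continuity correction | 0.191 | 0.096 |
| Fisher's exact | 0.191 | 0.095 |

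No two-sided version is near 0.05. The one-sided uncorrected value, 0.051, may be where the sentence came from, but the document does not say so, and E.9 rules it out.

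**Step 3: what would reach significance at 20 per group.** With 10/20 control failures:

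| nHFJV failures | Chi-square P | Fisher P |
|---|---|---|
| 5/20 (25%) | 0.102 | 0.191 |
| 4/20 (20%) | 0.047 | 0.096 |
| 3/20 (15%) | 0.018 | 0.041 |

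**Step 4: at what size an observed 50% versus 25% reaches 0.05.** For the chi-square test, setting z = 1.96 with pooled rate (0.50 + 0.25)/2 = 0.375:

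n per group = 1.96² × 2 × 0.375 × 0.625 / 0.25² ≈ 28.8.

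Among group sizes at which the two rates give whole counts:

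| n per group | Chi-square P | Fisher P |
|---|---|---|
| 20 | 0.102 | 0.191 |
| 24 | 0.074 | 0.135 |
| 28 | 0.053 | 0.097 |
| 32 | 0.039 | 0.070 |
| 36 | 0.028 | 0.0505 |
| 40 | 0.021 | 0.037 |

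**Step 5: power at the planned size.** Take each of the 21 × 21 possible tables, weight it by Binomial(20, 0.50) × Binomial(20, 0.25), and sum the weights of those with two-sided P < 0.05. This gives 0.375 for uncorrected chi-square and 0.269 for Fisher. The chance of a non-significant result is therefore 62.5% or 73.1%.

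**Step 6: precision.** The Wilson 95% limits are 29.9% to 70.1% for 10/20 and 11.2% to 46.9% for 5/20. Newcombe's interval for the 25-point difference is

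lower: 0.25 − √[(0.500 − 0.299)² + (0.469 − 0.250)²] = −0.047

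upper: 0.25 + √[(0.701 − 0.500)² + (0.250 − 0.112)²] = +0.494

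that is, about −5 to +49 percentage points.

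**The case against.** The wording is hedged. E.10 claims neither P = 0.05 nor significance; it says the result would come close, after two other qualifiers. With 20 per arm the P value moves in large steps, and one infant changes it a good deal: 10/20 versus 4/20 gives 0.047 and 11/20 versus 5/20 gives 0.053. The sentence names only chi-square, and with 7.5 expected failures per arm the usual small-cell reason for Fisher does not apply. The like-for-like gap is thus 0.10 against 0.05. The comparator and gestational age of the cited trial are already disclosed in section B, and the trial is a pilot whose size does not depend on this sentence.

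Much of this is fair as to weight. The Fisher figures are context for a sentence that names chi-square, though relevant context, because E.9 allows Fisher for the primary outcome. The point about the source of the rates is secondary. The pilot status limits the consequence.

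It does not rescue the figure. The rates as stated give exactly 10/20 and 5/20, and 0.10 is twice the threshold. The one-infant argument also runs the other way: 9/20 versus 5/20 gives P = 0.18.

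**Conclusion.** The figure is wrong as written. At the stated rates and size, the named test gives two-sided P = 0.10, and the plan's alternative test gives 0.19. The assumed result would be non-significant by both, and power for a true difference of that size is about 38% (chi-square) or 27% (Fisher).

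This rests on the two-sided rule in E.9, the uncorrected Pearson form of the chi-square test (a continuity correction raises P to 0.191), equal groups of 20 with no missing outcomes, and the 50% and 25% rates as the protocol gives them. The cited trial's own data were not available to check.

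The consequence is moderate. No test, endpoint or sample size depends on the sentence, but it is the only number offered for the possibility of showing a significant benefit. It should be corrected.

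**What to change.** Keep 40 infants and rest that number on feasibility and safety. In E.10, replace the P-value sentence with text such as:

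> With 20 infants per group, observed failure rates of 50% and 25% would give two-sided P = 0.10 (chi-square) or 0.19 (Fisher's exact test). Power for a true difference of this size is about 38% or 27%. The 95% confidence interval for the difference would be about −5 to +49 percentage points.

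Add that efficacy results will be reported as estimates with 95% confidence intervals, and that a non-significant result does not show lack of benefit. Add one clause saying that the trial cited for the 25%, and in part for the 50%, compared nasal high-frequency ventilation with nasal CPAP at a mean gestational age of about 32 weeks, so both rates are assumptions for this population.

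The cost is a wording amendment to E.10 and a small addition to the reporting plan in E.9. Sample size, tests, endpoints and conduct are unchanged. The price to the sponsor is a less favourable printed figure.
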